### 10.2 Handling of the Difference between the Scheduled and the Actual Sampling Times

The actual clock time for dosing and the actual clock time for each collection time for the PK samples will be recorded using electronic data capture. For all sampling times, the actual sampling times will be calculated as the difference between the sample collection actual clock time and the actual clock time of dosing. The actual post-dose sampling times expressed in hours and rounded off to three decimal digits will be used to calculate the PK parameters, except for pre-dose samples occurring prior to dosing, which will always be reported as zero (0.000), regardless of the time difference. Scheduled sampling times will be presented in concentration tables and mean graphs, while actual sampling times will be presented in the individual graphs in the PK section of the report. A listing of the actual times for PK sampling will be provided for PK samples.

### 10.3 Pharmacokinetic Parameters

PK analyses will be performed using Phoenix® WinNonlin® version 8.2, which is validated by Syneos Health. Inferential statistical analyses will be performed using Statistical Analysis System (SAS®) version 9.4 according to FDA guidelines. Bioanalysis of all samples should be completed prior to the initiation of the PK statistical analyses.

A total of 17 blood samples will be collected in each period for PK analyses: pre-dose and 0.133, 0.250, 0.500, 1.00, 1.50, 2.00, 3.00, 4.00, 5.00, 6.00, 8.00, 10.0, 12.0, 16.0, 24.0, and 32.0 hours post- dose.

#### Plasma PK Parameters

The following PK parameters will be calculated by standard non-compartmental methods with JOTROL (resveratrol) plasma concentrations:

#### Primary parameter:

AUC0-inf: Area under the concentration-time curve from time zero to infinity (extrapolated), calculated as  $AUC_{0-t} + C_t/K_{el}$ , where  $C_t$  is the last observed measurable concentration.

---

AUC 0-t :	Area under the concentration-time curve from time zero to the last measurable concentration. AUC 0-t will be calculated using the linear trapezoidal-linear interpolation method.
C max :	Maximum observed concentration.

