AUC _{inf} (ng h/mL)	4,049 (26.6)	10,053 (73.2)	16,984 (41.7)	30,898 (46.1)
C _{max} (ng/mL)	1,135 (25.7)	2,102 (81.3)	2,786 (27.2)	4,294 (48.0)
T _{max} (h)	1.500 (1.0-5.0)	2.000 (1.0-5.0)	2.000 (1.0-5.2)	2,050 (1.0-6.0)
C _{av} (ng/mL)	172.0 (23.2)	402.6 (70.5)	597.0 (27.0)	1,089 (49.4)
Half-life (h)	3.21 (56.6)	4.51 (82.8)	11.5 (95.5)	7.71 (42.3)
CL/F (L/h)	131.2 (25.8)	151.8 (62.7)	171.2 (40.0)	207.8 (63.9)

NOTE: Values are the mean of *n* = 10 with coefficient of variation (in percent) or range in brackets.

Abbreviations: AUC_{inf}, area under the concentration versus time curve to time infinity; C_{max}, maximal plasma concentration; T_{max}, median time of maximal plasma concentration; C_{av}, average plasma concentration; CL/F, apparent total body clearance (calculated as dose/AUC_{inf}); CL_R, apparent renal clearance approximated by amount excreted with urine within 24 h over AUC₀₋₂₄; V/F, apparent volume of distribution.

**n* = 1, value for AUC_{inf} at the lowest dose could be established in only one participant.

Figure 1 Mean Plasma Concentrations of Resveratrol (A), Two Resveratrol Monoglucuronides (B and C), and Resveratrol-3-sulfate (D) Versus Time in Healthy Volunteers Who Received a Single Dose of Resveratrol at 0.5, 1.0, 2.5, or 5.0 g Doses.

5. Objectives

The objectives of this study are:

- To characterize the PK profile of JOTROL (resveratrol) following oral administration of SAD ranging from 200 mg up to a dose currently estimated at 1000 mg, in healthy adult subjects;
- To evaluate the effect of food on the PK profile of JOTROL.

6. Study Design

This will be a single center, Phase 1, open-label, sequential SAD study, with a food-effect arm. The study will be divided into two parts:

- Study Part 1 consists of 3 periods with SAD of JOTROL under fasting conditions. Periods 2 and 3 will be initiated with updated doses after safety, tolerability, and PK data are evaluated by the Safety Committee **and the DSMB** and deemed acceptable for single doses for subsequent doses.
- Study Part 2 consists of a single oral JOTROL dose under fed conditions. JOTROL dose for this study part will derive from study Part 1 safety, tolerability, and PK data.

This study is intended for filing under FDA regulations.

7. Rationale for Dose Selection

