## 10. Pharmacokinetic Analyses

### 10.1 Handling of the Below the Lower Limit of Quantification (BLQ) and the No Reportable Concentration

All concentration values that are BLQ occurring prior to dosing as well as samples with no reportable value (NRV) occurring prior to dosing will be replaced by "0.00"; otherwise they (BLQ and NRV) will be set to missing for tabulation, graphical representation and calculation purposes.

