**Secondary parameters:**

Residual area:	Residual area, calculated as $100 \times (1 - AUC_{0-t} / AUC_{0-inf})$ .
T max :	Time of observed C max .
T ½ el :	Elimination half-life, calculated as $\ln(2) / K_{el}$ .
K el :	Elimination rate constant. This parameter will be the negative of the estimated slope of the linear regression of the ln-transformed concentration versus time profile in the terminal elimination phase. Best fit method will be used to calculate the K el from at least 3 concentration data points excluding the C max . Rsq adjusted, the goodness of fit statistic for the terminal elimination phase, adjusted for the number of points used in the estimation of K el must be $\geq 0.8$ . No points below T max will be used. If the K el cannot be measured (e.g.: fewer than 3 non-zero concentrations in the terminal elimination phase or Rsq adjusted < 0.8), the PK parameters derived from K el will not be reported for that individual PK profile (AUC 0-inf , Residual area, and T ½ el ). The timepoint where ln-linear K el calculation begins (K el Lower ) and the actual sampling time of the last measurable concentration used to estimate the K el (K el Upper ), as well as the Rsq adjusted for the ln-linear regression for the calculation of the elimination rate constant will be reported.

Additional PK analyses may be performed. Upon Sponsor's request, PK repeats might be performed according to Syneos Health's SOP. If re-assays are requested for PK reasons (not advised), final results will include re-assay values, while results with original values will be presented in an appendix of the clinical study report as supportive data. The rationale for re-assays for PK reasons must be provided.

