### 10.5.3 Criteria for Determination of Dose-Proportionality

PK dose proportionality will be concluded if the 90% C.I. of  $b$  for  $AUC_{0-inf}$ ,  $AUC_{0-t}$  and  $C_{max}$  are entirely contained within the following bounds that depend on the dose range ratio ([Smith BP, 2000](#)) (i.e.,  $\ln(1000/200) = \ln(5)$ ):

- Lower bound =  $1 + \ln(0.80) / \ln(5) = 0.861353116$  and
- Upper bound =  $1 + \ln(1.25) / \ln(5) = 1.138646884$

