**12. Handling of Missing Data**

For safety,

- If an AE is recorded with an onset date corresponding to a dosing day, but the time is missing, then the AE will be assigned to the treatment phase planned treatment with a dosing planned that day.
- If an AE is recorded with an onset date that does not correspond to a dosing day, but the time is missing, then the AE will be assigned to the treatment phase planned treatment that covers the AE onset day.
- If an AE is recorded with an onset date where day and time are both missing, then the AE allocation to a treatment phase planned treatment will be done on a case by case basis considering available information (e.g. AE onset date, AE end date, AE comments, subject disposition).

For PK, only observed data will be used in the data analysis except for concentration values BLQ as described in Section 10.1. No attempt will be made to extrapolate or interpolate estimates for missing data.

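### If the 200 mg profile falls below quantification before the higher doses, the AUC0-t slope is biased upward and can by itself block a conclusion of dose proportionality

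*SAP*

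**What the plan says.** SAP 10.3 makes AUC0-t a primary parameter, defined as "Area under the concentration-time curve from time zero to the last measurable concentration" and computed by linear trapezoids. SAP 10.1 sets pre-dose values below quantification to zero; for all later samples, "otherwise they (BLQ and NRV) will be set to missing for tabulation, graphical representation and calculation purposes". SAP 12 adds: "No attempt will be made to extrapolate or interpolate estimates for missing data".

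The other exposure parameter, AUC0-inf, is AUC0-t plus Ct/Kel. If Kel cannot be estimated (fewer than three terminal points, or adjusted Rsq below 0.8), the parameters derived from it "will not be reported for that individual PK profile". Residual area is reported, but no rule depends on it.

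SAP 10.5.2 fits a random-intercept power model to the three fasting periods. The decision rule in SAP 10.5.3 opens with "PK dose proportionality will be concluded if the 90% C.I. of" the slope and names AUC0-inf, AUC0-t and Cmax. All three intervals must lie within 0.861353116 to 1.138646884. No AUC over a common interval is planned.

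**The concern.** The power model compares areas across doses within a subject, but those areas need not cover the same time span. Concentrations at 200 mg are nominally one fifth of those at 1000 mg, so the low-dose profile can be expected to reach the assay limit first. The missing tail then makes the 200 mg area too small relative to the others, and the slope rises even when the drug is exactly proportional.

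The margin on either side of 1 is only 0.139, so a modest loss of area at one dose uses up much of it. The trial could then fail its own proportionality criterion because of the assay limit, and the SAP has no pre-specified analysis that separates this from a real departure.

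**Working it through.** **1. The plan's bounds.** 1 + ln(0.80)/ln(5) = 1 − 0.223144/1.609438 = 0.861353, and 1 + ln(1.25)/ln(5) = 1.138647. Both agree with SAP 10.5.3.

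**2. Slope bias from lost area.** With complete data at 200, 500 and 1000 mg, the power-model slope is a weighted sum of the log parameters. The weights are (ln dose − mean ln dose)/Σ(ln dose − mean)²:

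- ln doses: 5.298, 6.215, 6.908; mean 6.140
- sum of squared deviations: 0.709 + 0.006 + 0.589 = 1.303
- weights: −0.646, +0.057, +0.589

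If a fraction f of the true area is captured at each dose, then b = 1 + Σ w·ln f for a truly proportional drug. With 500 and 1000 mg complete:

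| Capture at 200 mg | b |
|---|---|
| 95% | 1.033 |
| 90% | 1.068 |
| 85% | 1.105 |
| 80% | 1.144 |

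The upper bound is reached when −0.646·ln f = 0.1386, so f = exp(−0.2147) = 0.807. If all doses lose some area (80, 90 and 95% captured), b = 1 + 0.144 − 0.006 − 0.030 = 1.108.

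**3. The SAP rules applied to proportional data.** The simulation used true b = 1, 24 subjects, the 17 planned sampling times, post-dose BLQ values set to missing, linear trapezoids, the SAP Kel rule, a random-intercept model with 90% CI, and 200 replicates. From Protocol Table 1 (unmodified resveratrol) come the Cmax of 72.6 ng/mL at 0.5 g and the half-lives of 2.85 h and 8.87 h. These are assumptions: the LLOQ, the profile shapes, a 1 h fast phase, between- and within-subject log SDs of 0.45 and 0.22, and 8% assay noise. Cells show mean b, with the percentage of trials inside the bounds on that parameter.

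| Profile | LLOQ (ng/mL) | AUC0-t | AUC0-inf | Common-window AUC |
|---|---|---|---|---|
| Mono-exponential, 2.85 h | 0.1 | 1.008 (80%) | 1.004 (82%) | 1.000 (84%) |
| | 1 | 1.018 (70%) | 0.996 (79%) | 0.992 (82%) |
| | 2 | 1.044 (59%) | 1.004 (88%) | 0.999 (92%) |
| | 5 | 1.109 (15%) | 0.993 (80%) | 0.995 (89%) |
| Bi-exponential, 1 h and 8.87 h | 0.1 | 0.998 (83%) | 0.998 (82%) | 0.998 (83%) |
| | 1 | 1.045 (60%) | 1.006 (84%) | 0.996 (92%) |
| | 2 | 1.114 (15%) | 1.032 (64%) | 0.997 (88%) |
| | 5 | 1.257 (0%) | 1.138 (7%) | 0.994 (89%) |

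The Monte Carlo error of a pass rate near 80% is about √(0.8 × 0.2/200) = 2.8 points, so small differences mean nothing. The common window runs to the shortest Tlast across the subject's fasting periods.

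**4. Range over exposure.** Parent AUC at 1000 mg was varied from 545 ng·h/mL (Table 1 gives 544.8 at 1.0 g) to 2,000 ng·h/mL, just under the protocol's ceiling of 2.1 µg·hr/mL. Noise-free profiles with LLOQ 0.1 to 5 ng/mL gave AUC0-t slopes of 1.00 to 1.30, and exactly 1.000 with the common window. A separate 24-subject simulation with LLOQ 1 to 5 gave mean slopes of 1.02 to 1.22. When the step 3 concentrations were raised five-fold without noise, an LLOQ up to 2 ng/mL gave at most 1.02.

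**5. AUC0-inf.** With a log-linear tail, Ct/Kel restores the lost area and b stays at 0.993 to 1.004. It rises only when the slow phase is lost at 200 mg and Kel is taken from the steeper early phase. In one noise-free case of this kind (LLOQ 2; Tlast 6, 16 and 24 h), b was 1.133 while the 200 mg residual area was only 9.6%.

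**The case against.** The strongest objection is that the size is unknown and may be nil. The documents give no LLOQ and no JOTROL concentrations, and the formulation is designed to raise exposure. At the higher exposures examined, with a sensitive assay, the bias is negligible. This stands, and it is why a range is given.

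The consequence is also limited. Protocol 12.3 calls all inference exploratory, SAP 10.5.3 has no rule for declaring a more-than-proportional increase, and SAP section 7 bases dose selection on descriptive interim PK rather than on b. That lowers the stakes, but 10.5.3 still fixes a pass/fail rule that AUC0-t can fail through truncation. The general allowance for additional analyses pre-specifies nothing.

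Two stronger readings are tempting, and the documents support neither:

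- A reader might infer that AUC0-inf is biased upward because it has no extrapolation limit. Step 5 shows that the limit is not the cause. Excluding residual areas above 20% can do harm: in the mono-exponential case at LLOQ 5 it moved b from 0.993 to 0.945, cut the pass rate from 80% to 40% and lost 40% of the 200 mg values. In the bi-exponential case 70% of the 200 mg values were lost and b was still 1.077.
- A reader might take Protocol Table 1 as proof, since AUCinf "at the lowest dose could be established in only one participant". That footnote concerns 0.5 g of unmodified resveratrol, gives no cause and says nothing about AUC0-t. It makes early loss of quantification plausible for the parent only. The three metabolites carry no such note, and their Cmax at 0.5 g is 369.5 to 1,135 ng/mL against 72.6 for the parent.

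Nor is a separate count of missing AUC0-inf values needed, because SAP 10.5.1 already reports the number of observations by treatment.

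**Conclusion.** The point holds for AUC0-t, conditionally. If 200 mg loses a larger share of its area to the assay limit than the higher doses do, b is biased upward: by 0.07 at 90% capture, and by the whole margin at about 81%. These two figures are pure arithmetic and assume only that the higher doses are complete. Whether such losses will occur cannot be read from the documents. Under the assumed LLOQ and exposure ranges, b lies between about 1.00 and about 1.2–1.3, with the upper end requiring low exposure and an insensitive assay. The risk is mainly for parent resveratrol.

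AUC0-inf is not biased by the lack of an extrapolation limit, only by loss of the slow terminal phase at 200 mg. Since the inference is exploratory, this is an inexpensive improvement to the plan and not a critical defect.

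**What to change.** In SAP 10.5.2, pre-specify a supportive power-model fit on AUC from zero to the shortest Tlast across that subject's fasting periods. Define the end of the window by scheduled sample, stepping back to the latest sample that all those periods share, so that no interpolation is needed. In SAP 10.5.3, state that the AUC0-t criterion is read together with this fit. A failure on the high side that disappears over the common window would be reported as compatible with truncation.

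Residual areas above 20% may be flagged in the listings, but those values should stay in the power model and in the food-effect ANOVA.

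The cost is SAP wording, one derived parameter and one further model run, with no new samples or visits. The drawback is that the common window omits part of the tail and would miss non-proportionality confined to late times. It therefore supports AUC0-t and does not replace it.

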**Secondary parameters:**

Residual area:	Residual area, calculated as $100 \times (1 - AUC_{0-t} / AUC_{0-inf})$ .
T max :	Time of observed C max .
T ½ el :	Elimination half-life, calculated as $\ln(2) / K_{el}$ .
K el :	Elimination rate constant. This parameter will be the negative of the estimated slope of the linear regression of the ln-transformed concentration versus time profile in the terminal elimination phase. Best fit method will be used to calculate the K el from at least 3 concentration data points excluding the C max . Rsq adjusted, the goodness of fit statistic for the terminal elimination phase, adjusted for the number of points used in the estimation of K el must be $\geq 0.8$ . No points below T max will be used. If the K el cannot be measured (e.g.: fewer than 3 non-zero concentrations in the terminal elimination phase or Rsq adjusted < 0.8), the PK parameters derived from K el will not be reported for that individual PK profile (AUC 0-inf , Residual area, and T ½ el ). The timepoint where ln-linear K el calculation begins (K el Lower ) and the actual sampling time of the last measurable concentration used to estimate the K el (K el Upper ), as well as the Rsq adjusted for the ln-linear regression for the calculation of the elimination rate constant will be reported.

Additional PK analyses may be performed. Upon Sponsor's request, PK repeats might be performed according to Syneos Health's SOP. If re-assays are requested for PK reasons (not advised), final results will include re-assay values, while results with original values will be presented in an appendix of the clinical study report as supportive data. The rationale for re-assays for PK reasons must be provided.

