12.1.2 PK Parameters Calculated With Urine Concentrations

Urine samples will be used to calculate the following parameters for resveratrol, resveratrol-3-glucuronide, resveratrol-4'-glucuronide, and resveratrol-3-sulfate:

- 1) Ae_{0-t} : cumulative urinary excretion from time zero to time t, calculated as the sum of the amounts excreted over each collection interval. The amount excreted in urine for each time interval is calculated as the urine concentration multiplied by the urine volume.
- 2) R_{max} : maximum rate of urinary excretion, calculated by dividing the amount of drug excreted in each collection interval by the time over which it was collected.
- 3) T_{max} : time of R_{max} , calculated as the midpoint of the collection interval during which R_{max} occurred.

Additional PK analysis may be performed. Upon the Sponsor's request, PK repeats might be performed according to Syneos Health's SOP. If re-assays are requested for PK reasons, final results will include re-assay values, while results with original values will be presented in an appendix of the clinical study report as supportive data.

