### 3.6 Randomization and Blinding

Subjects will be administered 200 mg, 500 mg and 1000 mg gelcaps sequentially in ascending order. As this is an open-label study no blinding will be applied.

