## 7. Interim Analyses

Interim PK analyses will be performed between each dose level and will inform selection of the subsequent dose. The Interim Analyses using PK concentration data will be done after the bioanalytical phase is completed and will include data from subjects who have finalized their study visits at the time of the interim database availability.

PK parameters will be calculated using scheduled sampling times as actual sampling times will not be available for these interim analyses. Only descriptive statistics will be calculated and provided. Interim descriptive analyses of the PK variables will be conducted for each period (Number of observations [N], arithmetic mean, standard deviation [SD], coefficient of variation [%CV], median, minimum [Min], maximum [Max], geometric mean, and %CV geom.mean).

---

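### Re-assays requested for PK reasons supply the final results with no stated selection rule, so values could be replaced because of what they show

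*SAP*

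**What the plan says.** SAP section 10.3, at the end of the secondary parameters, permits repeats at the sponsor's initiative: "Upon Sponsor's request, PK repeats might be performed according to Syneos Health's SOP". It then fixes which value counts: "If re-assays are requested for PK reasons (not advised), final results will include re-assay values". Two safeguards follow. The first concerns the originals: "while results with original values will be presented in an appendix of the clinical study report as supportive data". The second is a duty to explain: "The rationale for re-assays for PK reasons must be provided".

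Protocol section 12.1.2 carries the same hierarchy: "If re-assays are requested for PK reasons, final results will include re-assay values, while results with original values will be presented in an appendix". It also refers to the CRO's SOP. It neither discourages the practice nor asks for a rationale.

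The setting matters. SAP 3.6 states "As this is an open-label study no blinding will be applied", and SAP 7 states "Interim PK analyses will be performed between each dose level and will inform selection of the subsequent dose". Under protocol 7.5 the Safety Committee, which reviews PK data before each escalation, includes a medically qualified sponsor representative. SAP 10.3 asks that bioanalysis be finished before the PK statistical analyses begin. Protocol 12.3 describes all inference as exploratory.

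**The concern.** A re-assay for PK reasons means, on an ordinary reading, that somebody looked at a concentration or profile and found it implausible, without an analytical failure having been recorded. If only unexpected values are challenged, the set of replaced values is selected on the outcome. A fresh assay draw for an extreme value tends to fall nearer the centre, so the spread shrinks. If challenges run mostly in one direction, the mean moves too.

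The replaced values would feed two explicit decision rules in the SAP. Section 10.5.3 concludes dose proportionality if the 90% interval for the slope lies within 0.861 to 1.139. Section 10.5.4 concludes no food effect if the 90% intervals lie within 80.00% to 125.00%. The SAP itself advises against the practice, yet gives its product precedence in the final results.

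**Working it through.** **What the documents fix and leave open**

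| Element | SAP 10.3 | Protocol 12.1.2 |
|---|---|---|
| Sponsor may request repeats | yes | yes |
| Repeat value is final | yes | yes |
| Original-value results in appendix | yes | yes |
| Practice discouraged | yes | no |
| Rationale required | yes | no |
| Criterion for choosing samples | none | none |
| Limit on number of samples | none | none |
| Cut-off relative to seeing PK results | none | none |
| Independent decision-maker | none | none |

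SAP section 4 records no change from the protocol in planned analyses, so the two texts should agree.

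**Size: inputs.** The plan has no figure of its own on this point. From the documents: 16 subjects in Part 2 (SAP 3.5), a 90% interval, and margins of 80.00% to 125.00% (SAP 10.5.4). Assumed, because the documents do not give them: within-subject SD on the log scale 0.25 to 0.35 per period; assay SD 0.05 to 0.15; 2 of 16 pairs re-assayed in both periods; re-assay error independent with the same SD; a parameter resting on a single concentration, such as Cmax.

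**Method.** For subject i the log difference is d_i = (fed − fasting), with biological and assay error in each period. The interval is mean(d) ± t(0.95, 15 df) × SD(d)/√16. In each of 40,000 simulated trials the two chosen pairs receive a fresh assay error, and the interval is recomputed.

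**Results**

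| Selection | Assay SD | Interval width, new/old | Coverage (nominal 90%) | Ratio estimate (true 1.00) |
|---|---|---|---|---|
| 2 most extreme pairs | 0.10 to 0.15 | 0.917 to 0.974 (3 to 8% narrower) | about 86 to 89% | 1.00 |
| 2 most extreme pairs | 0.05 | 0.987 to 0.993 | 89.4 to 89.8% | 1.00 |
| 2 highest ratios | 0.10 to 0.15 | – | – | about 0.98 to 0.99 |

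If assay error is counted inside the within-subject SD rather than added to it, narrowing is 3 to 11% and coverage 85 to 89%.

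**Wider stress range.** This used 60,000 runs, within-subject CV of 20, 30 or 50%, assay CV of 5, 10 or 15%, and 2 or 4 of 16 re-assayed. Two-sided selection gave width ratios of 0.855 to 0.996 and coverage of 83.1 to 89.8%. The lower ends come from within-subject CV 20%, assay CV 15% and 4 of 16 re-assayed. Re-assaying the 4 highest ratios (within-subject CV 20 or 30%, assay CV 5 or 15%) when the true ratio is 1.25 gave estimates of 1.203 to 1.245. The chance of wrongly concluding no food effect rose from 3.4–5.1% to 4.8–13.5%.

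**Limits.** If samples were chosen at random, or by a rule independent of the observed value, the interval's properties would not change. AUC averages assay error over many samples, so it should be less affected. The dose-proportionality slope was not simulated; only the direction of the effect carries over.

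**The case against.** The strongest counter-case has five parts.

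- **Safeguards exist.** Repeats follow an SOP, the SAP demands a rationale, and results with original values must be reported, so a reader can see the impact. This stands, and it limits the harm. It does not settle which values carry the stated conclusions, and a rationale is not a pre-set trigger: an implausible profile would satisfy it.
- **Criteria may sit in the SOP.** Its content is not in the documents, so their silence does not show that no criteria exist. This stands. The point is that neither document states or cites a criterion.
- **Timing and effect are possibilities.** A reader might infer that the sponsor will request repeats after seeing the results, and that the intervals will therefore be too narrow. The documents do not support that. No section says when requests are made, and none prescribes choosing extreme values. They leave both open: completing bioanalysis before the statistical analyses does not rule out a later repeat, and interim PK is seen between dose levels.
- **Large shifts do not show harm.** With 16 pairs, one Cmax changed f-fold moves the ratio by f^(1/16): 2^(1/16) = 1.044 and 3^(1/16) = 1.071; two such changes give 1.091 and 1.147. A reader might take 4.4 to 14.7% as the size of the problem. But with assay SD 0.10 to 0.15, a 2-fold disagreement between two assays is ln 2/(√2 × SD) = 4.9 to 3.3 standard deviations, and a 3-fold one is 7.8 to 5.2. Such a gap implies gross error in one value, possibly the original, in which case the repeat removes bias.
- **The simulation is a proxy.** It selects on the fed/fasting ratio, whereas a PK reason would usually concern one profile in one period. This stands as a limit on the figures.

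A reader might also infer that interim dose decisions would be undermined. Interim and final exposures can differ anyway, because SAP 7 uses scheduled times and SAP 10.2 actual times.

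**Conclusion.** The concern holds as a gap in the rule. The plan permits outcome-dependent replacement and lets its product drive the food-effect and dose-proportionality conclusions. The protocol is also weaker than the SAP, because it lacks the rationale requirement.

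The effect on the food-effect interval is modest, and its size rests wholly on assumed assay error, within-subject variability and number of re-assays. It runs from negligible at assay SD 0.05 to 3 to 8% narrowing and 86 to 89% coverage at assay SD 0.10 to 0.15 with two pairs re-assayed. One-sided selection adds a bias of about -1% to -2%. Larger effects need heavier or strongly directional re-assay. The exploratory status and the original-value appendix lower the stakes but do not change which values decide. This is a worthwhile, inexpensive improvement; it is not evidence that results will be distorted.

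**What to change.** Amend SAP 10.3 and protocol 12.1.2 in the same words:

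1. Original reportable values feed the primary tables, the power model and the food-effect ANOVA, unless an analytical cause is documented before the repeat result is known.
2. Any other re-assay for PK reasons is reported as a sensitivity analysis.
3. Every such re-assay is listed with old value, new value and reason.
4. The protocol takes over the SAP's rationale requirement.

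The cost is wording only; no data collection changes. The downside is that a true assay outlier with no documented cause stays in the primary analysis, with the sensitivity result beside it.
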